3.2 Study Population

3.2.1 Inclusion criteria

1. Age 18-60 years
2. Active alcohol use disorder (with last alcoholic drink within 8 days of randomization)

3.2.2 Exclusion criteria

1. Any active and uncontrolled medical problem(s)
2. Known zinc deficiency
3. Primary substance of abuse something other than alcohol
4. Current abnormal chest x-ray
5. HIV-positive
6. Any disorder of blood coagulation
7. Currently on medical treatment with anti-coagulants (including warfarin, heparin, direct thrombin inhibitors, or anti-platelet agents)
8. Daily use of vitamins or other nutritional supplements (Clarification: patients who are prescribed vitamins as part of their treatment for alcohol abuse will not be excluded and will be allowed to continue their prescribed vitamins throughout the study. Only patients on daily vitamin supplements prior to screening will be excluded.)
9. Renal impairment (GFR < 60)
10. Active bipolar disorder
11. Active Parkinson's disease
12. Current pregnancy
13. Contraindication to treatment with zinc or S-adenosylmethionine
14. Inability to give informed consent (i.e., limited cognitive capacity)
15. Non-English speaking

3.3 Randomization

A statistician who is otherwise uninvolved with this study will provide a randomization list, which will be prepared using a computer-based pseudo-random number generator. Our scheme will be permuted-block randomization with a block size of 8 and an allocation ratio of 2:2:2:2. Based on pilot information, we expect a minority (10-15%) of participants to be non-smokers. To ensure equivalent representation of smoking and non-smoking subjects in each group, we will stratify randomization on current smoking status. After the patient is

enrolled in the study, but prior to randomization, he/she will undergo an initial bronchoscopy procedure. The randomization will occur only after this initial bronchoscopy procedure. The patient will be assigned to one of four treatment groups based on the randomization list.

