3.1.1 Power and sample size calculations

The primary outcome for this clinical trial will be the phagocytic index of the alveolar macrophage before and after at least 14-days of treatment. Phagocytic index is the most relevant primary outcome as it is a well-established marker of immune function and its improvement with either zinc treatment or SAME treatment would indicate reversal of the alcoholic lung phenotype. Secondary outcomes will include change in GM-CSF receptor expression in the alveolar macrophage, change in alveolar macrophage zinc levels (signifying improvement of alveolar zinc deficiency), and change in redox potential [as measured by ratios of the redox couples glutathione/glutathione disulfide (GSH/GSSG) and cysteine/cysteine (Cys/Cyss) in the BAL and EBC fluid].

For the power calculations, we used data from previous animal studies, in which the estimated standard deviation for change in phagocytic capacity is between 0.2 (20%) and 0.40 (40%) depending on baseline values versus follow-up values, respectively. We assume a correlation coefficient of 0.85 between baseline and 14-day follow-up values within a treatment group. Given inherent variability in human data compared to animal data, our assumption will be that the separation of groups will not be as robust. Therefore, we took these predictions, as well as our some of our preliminary data in human subjects, into consideration when calculating sample size requirements. Assuming that we will detect on average a 30% increase in treated (zinc and/or SAME supplemented) subjects and on average no change in the untreated subjects, a sample size of 19 alcoholics in each group will ensure statistical power exceeding 80% to detect a treatment difference of 30% at the 2-sided 5% significance level if the true difference between groups is 30%. However, in order to account for limitations including dropout and inadequacy of sampling, we will use a sample size of 25 subjects in each group (dietary zinc, dietary SAME, and placebo) for a total of 100 subjects randomized for the entire study. This additional recruitment will ensure adequate statistical power is maintained at the completion of the study.

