3.1.3 Test statistic for the primary null hypothesis

The primary null hypothesis will be tested in an intent-to-treat analysis using ANOVA to compare in phagocytic function across the four treatment groups.

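### Randomisation is stratified on smoking, but the stated primary ANOVA names no smoking term; if smoking predicts the analysed outcome, the test is conservative and loses some power

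*Combined protocol and SAP*

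**What the plan says.** Section 3.3 (Randomization) sets out "permuted-block randomization with a block size of 8 and an allocation ratio of 2:2:2:2". It adds that "we expect a minority (10-15%) of participants to be non-smokers" and, for that reason, "we will stratify randomization on current smoking status". Smoking is the only stratification factor.

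The primary analysis is one sentence in section 3.1.3: "The primary null hypothesis will be tested in an intent-to-treat analysis using ANOVA to compare in phagocytic function across the four treatment groups". It names no stratum term, baseline covariate or other adjustment. Section 8, despite its heading on statistical considerations, covers data capture and software and adds no model.

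Section 3.1.1 describes the primary outcome as the "phagocytic index of the alveolar macrophage before and after at least 14-days of treatment" and powers the trial on an SD for change. Section 3.1.3 does not say whether the ANOVA compares change or the follow-up value.

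**The concern.** Stratified blocking removes most of the between-arm difference in smoking, so the true variance of an arm comparison excludes most of the smoking effect. An ANOVA on treatment alone does not take account of this: it puts the smoker/non-smoker difference into the residual. The estimated standard errors are then larger than the real ones, the F-test falls below its nominal 5%, and power is given up.

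The plan treats smoking as important enough to stratify on, then does not say that it will be used in the analysis. What is at stake is efficiency, not validity. The condition also concerns the variable actually analysed: smoking must predict the 14-day change, or the follow-up value if that is what is compared.

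**Working it through.** **Inputs from the documents.** Non-smokers 10–15% (section 3.3). Blocks of 8, four arms in equal ratio (3.3). Two-sided 5% level, effect 0.30 in treated arms and 0 in placebo, 19 evaluable and 25 randomised per arm (3.1.1), so N = 76 and N = 100. SDs 0.2 and 0.40, correlation 0.85 (3.1.1).

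**Assumption.** The documents give no smoking effect. Let D be the smoker/non-smoker difference in the analysed outcome, in within-stratum SDs, with range 0 to 1.5.

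**The plan's own sample size.** Reading 0.2 and 0.40 as the baseline and follow-up SDs:

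- SD of change = √(0.2² + 0.4² − 2 × 0.85 × 0.2 × 0.4) = √0.064 = 0.253.
- n per arm = 2 × (1.960 + 0.842)² × 0.064 / 0.30² = 11.2, so 12, not 19.
- Solving the same formula for n = 19 gives an SD of 0.33, which the document does not state.

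Section 3.1.1 says human preliminary data, not reported, also informed the number, so 19 cannot be fully checked. I therefore show power at both 0.33 and 0.253.

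**Step 1: standard error.** With non-smoker proportion p, the error variance without the term is inflated by v = 1 + p(1 − p)D². The standard error is too large by √v − 1, and the information lost is 1 − 1/v.

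| D | v (p = 0.125) | SE too large | SE range, p = 0.10 to 0.15 | Information lost (p = 0.125) |
|---|---|---|---|---|
| 0.5 | 1.027 | 1.4% | 1.1–1.6% | 2.7% |
| 1.0 | 1.109 | 5.3% | 4.4–6.2% | 9.9% |
| 1.5 | 1.246 | 11.6% | 9.7–13.4% | 19.7% |

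**Step 2: type I error.** If the strata were perfectly balanced, the real size would be about P(F > v × critical value). For N = 100 the critical value of F on 3 and 96 degrees of freedom is 2.70. At D = 1.0 the probability of exceeding 1.109 × 2.70 = 2.99 is 3.5%.

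Simulating the stratified blocks of 8 (80,000 null trials per setting, p = 0.125, N = 76 and 100) agrees:

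| D | Size without the term | Size with the term |
|---|---|---|
| 0 | 4.9–5.0% | 4.9–5.0% |
| 0.5 | 4.7% | 5.0% |
| 1.0 | 3.5–3.7% | 4.9–5.1% |
| 1.5 | 2.4% | 5.0–5.1% |

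With unstratified blocks the same unadjusted ANOVA stays at 4.9–5.1%. The shortfall therefore comes from stratifying and then leaving the factor out.

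**Step 3: power.** Arm means 0/0.30/0.30/0.30, p = 0.125, without v with the term (40,000 trials per setting at SD 0.33, 20,000 at 0.253):

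| D | N = 76, SD 0.33 | N = 100, SD 0.33 | N = 76, SD 0.253 |
|---|---|---|---|
| 0 | 81.3 v 81.1% | 91.2 v 91.2% | 96.9 v 96.9% |
| 0.5 | 79.9 v 80.9% | 91.0 v 91.5% | 96.6 v 96.9% |
| 1.0 | 76.2 v 80.8% | 88.9 v 91.6% | 95.4 v 96.8% |
| 1.5 | 70.0 v 80.8% | 84.1 v 91.1% | 92.9 v 96.6% |

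These SDs are within-stratum. If 0.33 is instead the total SD, already containing the smoking variance, unadjusted power at N = 76 stays near 81% and the term raises it to 81.9%, 85.1% and 89.1% for D = 0.5, 1.0 and 1.5.

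**Step 4: does analysing change remove the issue?** With SDs 0.2 and 0.4, correlation 0.85, and a smoking shift of 0.4 at both visits (N = 100, 6,000 trials), unadjusted size is 5.3% when change is analysed, within simulation error of 5%. It is 3.9% when the follow-up value is analysed.

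**The case against.** The strongest counter-argument is that the harmful settings need an implausibly large smoking effect. At an SD of 0.33, D = 1.0 is a difference of 0.33 and D = 1.5 is about 0.50, against a whole planned treatment effect of 0.30. If change is analysed, smoking would have to move the 14-day change by more than the supplements are expected to, and nothing in the documents suggests that. Section 3.1.1 leans towards change, and a constant smoking shift then cancels.

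The size of the loss also depends on the SD. At 0.253, which the stated inputs imply, the loss at 19 per arm is at most about 4 points and power stays above 90%. If the planning SD is a total SD, omitting the term forgoes a gain rather than creating a shortfall against the plan. Finally, section 3.1.3 is a single sentence; it does not state a smoking term, but it does not exclude one either.

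All of this stands as a limit on the size of the problem. It does not remove the problem: section 3.1.3 leaves the analysed variable open, smoking may affect change as well as level, and no setting examined made adjustment worse by more than simulation error.

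**Conclusion.** The concern holds, as a minor one. The plan stratifies on smoking and states a primary test without it. If smoking predicts the analysed outcome, the test is conservative. It is not anti-conservative, and the treatment estimates are not biased.

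At 19 per arm with a within-stratum SD of 0.33 and 10–15% non-smokers, the power lost is about 1 point at D = 0.5, 3 to 5 points at D = 1.0 and 9 to 13 points at D = 1.5. It is less with 25 completers per arm or a smaller SD. It is nil if smoking has no effect on what is analysed. These figures rest on the assumed range for D and the assumed pattern of equal benefit in all three active arms. The direction does not depend on the choice of SD, nor on whether 19 per arm can be reproduced.

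**What to change.** In section 3.1.3, state that the primary model includes treatment group and current smoking status, the stratification factor, as fixed terms. Say there too whether the response is change or the follow-up value, since that decides how much the term can matter. The document gives no model for the secondary outcomes; when one is written, include the same term.

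The cost is one term in the model statement and one degree of freedom. Smoking status is already needed for randomisation, so no new data are required. With no smoking effect, the term changed simulated power by 0.2 points or less. Making the change before unblinding also avoids a later, data-driven choice of covariate.

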3.4 Blinding

Treatment assignment will be masked to investigator, analyzing statistician, study staff, and subject. Only the dispensing pharmacist and the statistician who provides the randomization list will be aware of the treatment assignment.

4. **Drugs and Dosages**

4.1 Study Medications

There are a total of four treatment groups, and each randomized patient receives two types of pills. The first medication is either a tablet containing 50 mg of elemental zinc (zinc sulfate), or an identical appearing placebo tablet. The second medication is either 400 mg S-adenosylmethionine (S-AMe), or an identical appearing placebo tablet. Patients assigned to the combination treatment arm will receive both active medications (i.e., zinc and SAM), and those assigned to the placebo arm will receive placebo tablets only. The remaining two groups will receive one placebo and one active medication (i.e., either zinc or S-AMe).

4.2 Medication Administration

4.2.1 Zinc sulfate

A zinc sulfate tablet (containing 50 mg elemental zinc) or identically appearing placebo will be taken once daily for a total of two weeks. This medication can be taken at the same time as the other study medication below (i.e., S-AMe). After randomization, subjects will receive 14+ tablets of active zinc or placebo, which is enough to complete the minimum 14-day course of therapy until the repeat bronchoscopy procedure can be performed.

4.2.2 S-Adenosylmethionine

A 400 mg tablet of s-adenosylmethionine (S-AMe) or identically appearing placebo will be taken twice daily for a total of two weeks. This medication can be taken at the same time as the other study medication. After randomization, subjects will receive 28+ tablets of active S-AMe or placebo, which is enough to complete the minimum 14-day course of therapy until the repeat bronchoscopy procedure can be performed.

4.3 Storage and Handling of Medications

The trial medications will be stored in a locked area with limited access. The investigational drug services at the VA will be responsible for maintaining an inventory of study medication. The study coordinator and investigators will distribute the medications after the pharmacist dispenses it. In the event of any emergency, the investigational drug services at the VA (including the dispensing pharmacist) will be able to break the blind. The study medication will not be used for any purpose other than this study.

4.4 Concomitant Medications

In general, the supplements used in this study are safe, but there may be a potential for some drug interactions. First, zinc salts may alter the absorption of some antibiotics, and this caution will be communicated with the participants. A full review of patient medication will be done prior to the study. The subjects in this study will be otherwise healthy, so we expect there to be minimal use of other medications. We will also advise patients not to take any other nutritional supplements during the time that they are in this trial as not to complicate the study. Second, SAME is also a safe, readily available nutritional supplement, but can cause problems for patients with bipolar disorder and Parkinson's disease. Such subjects will be excluded from the study.

5. Trial Procedures

5.1 Recruitment and Pre-Screening

Study recruitment will primarily occur at the Atlanta VA Substance Abuse Treatment Program (SATP) clinic. IRB-approved recruitment posters will be displayed, and study brochures will be utilized. Interested patients will be pre-screened either by telephone evaluation or face-to-face during clinic visit with SATP provider. The purpose of the pre-screening is to identify patient who meet inclusion criteria and do not have any exclusions (listed in section 3.2). IRB-approved patient recruitment letters may also be utilized.

Recruitment will also occur in other parts of the VA hospital. Study brochures will be placed in VA clinics and other patient care areas. Interested patients may self-refer for the study by calling the study staff directly.

5.2 Baseline Visit

At (or prior to) the baseline visit, the study investigators in conjunction with the study coordinator will:

- Recheck to ensure that the patient meets all inclusion criteria and none of the exclusion criteria for the study (listed in section 3.2).

- **Obtain informed consent:**
 - o Written informed consent will be obtained from each patient prior to performing any baseline evaluations. In certain instances the coordinator may ask screening questions to determine eligibility for the study, but no actual evaluation will take place prior to obtaining informed consent. A copy of the signed informed consent is given to the patient, and the study coordinator retains the original and has it sent to medical records for scanning. The informed consent document will be reviewed and approved by the Institutional Review Board as well as the Atlanta VA Medical Center Research and Development Committee prior to the initiation of the trial.
- Collect baseline demographic information and medical history.
- Obtain AUDIT and SMAST questionnaires on participants to grade alcohol consumption (see appendix 2 and 3).
- Obtain Drinking History Questionnaire, Alcohol Dependence Scale (ADS), Food Frequency Questionnaire (FFQ), and Timeline Followback Form-90 to better understand the drinking pattern. (see appendix 4-8; appendix 7 is provided to participants to define “standard drinks”)
- Perform a physical examination.
- Order a chest x-ray (if one is not available from the past one year prior to enrollment).
- Collect urine for pregnancy testing (in women of childbearing age).
- Compensate the subject for the baseline visit with cash.

In certain instances, the patient will also undergo the bronchoscopy procedure described below on the same day as the baseline visit, but this would need to be scheduled in advance as the patient is required to not eat or drink anything for a minimum of 6 hours prior to the procedure. The actual randomization into treatment group will occur only after the initial bronchoscopy is done since the treatment follows the initial procedure. A schematic of the schedule of assessments is shown in appendix 1.

5.3 Bronchoscopy Procedure

5.3.1 Technical Procedure

- Study participants must not eat or drink anything for a minimum of 6 hours prior to the procedure. Prior to each bronchoscopy, blood will be collected for serum zinc, blood alcohol, biomarker testing, and measurement of redox stress. Urine will be collected for the presence of recreational drugs and ethyl glucuronide. Exhaled breath condensate will also be collected (described in section 5.4).

Patients will undergo a flexible fiberoptic bronchoscopy with standardized bronchoalveolar lavage (BAL) technique (180 ml of isotonic saline in a sub-segment

of the right middle lobe or lingula) using standard conscious sedation techniques. Lidocaine will be used for topical anesthesia. To ensure safety, participants will be closely monitored during the procedure per the routine protocol in the hospital bronchoscopy suite. Bronchoscopy is a common procedure performed at the Atlanta VA Medical Center for clinical and research purposes with a published complication rate of less than 0.5% and 0% mortality rate.³³ The bronchoscopy will be supervised by one of the study investigators or an attending physician with credentials to perform the procedure. Subjects will be monitored for up to 4 hours after completion of the procedure per standard conscious sedation recovery protocol until fully recovered. An optional “no sedation” bronchoscopy will be considered when requested by the patient. The usual post-procedure recovery period would not be required for cases done without sedation. For the initial bronchoscopy, subjects will be randomized after the procedure and given the study medication prior to discharge. Study volunteers will be compensated with \$25 cash for each study visit and either a check or direct deposit after each bronchoscopy procedure. In addition, the study team will offer a \$5 VA canteen voucher to the volunteer’s driver (the friend or family member who must accompany the volunteer to the procedure).

5.3.2 Measurements

BAL fluid will be processed and a standard cell count and leukocyte differential will be determined. BAL fluid will be separated into cell component (i.e., alveolar macrophage isolation) for assays of zinc, GM-CSF receptor expression, and function (phagocytic index). The supernatant will be aliquoted and frozen at -70C for assays of Glutathione (GSH/GSSG), Cysteine (Cys/CySS). All experiments performed are common research protocols within our Alcohol research group. The excess cells and BAL fluid, if any, will be frozen for future analysis. After all enrollment and analyses are completed and all record-keeping requirements expire, all collected samples will be discarded.

5.4 Exhaled Breath Condensate Collection

5.4.1 Technical procedure

After the participant has abstained from food and beverages for at least one hour, they will rinse their mouth with distilled or de-ionized water. Participants will be seated upright, and breathe normally in and out through the mouthpiece. The mouthpiece is connected to an exhaled breath condensate (EBC) collection tube, called the R-tube, which consists of a plastic tube placed inside a chilled cooling sleeve. The total collection period, with the patient breathing normally through the

mouthpiece, is approximately 10–15 minutes. After the collection session, an evacuation plunger is utilized to collect the sample and a pipette is used to aliquot samples into 1 ml tubes. The samples are stored at –70° C until analyzed.

5.4.2 Measurements

The EBC samples will be analyzed for oxidative stress through the measurement of redox pairs of Glutathione (GSH/GSSG) and Cysteine (Cys/CySS). These particular measurements are feasible and have previously been done in similar studies of alcoholic patients.³²

5.5 Follow-up Visits

Patients will have up to two follow-up visits during the two weeks that they are randomized to receive a study medication. These follow-up visits will occur prior to the second bronchoscopy procedure. In general, the first follow-up visit will occur sometime during the first week of therapy, and the second follow-up visit will occur sometime during the second week of therapy. At the discretion of the PI, the second follow-up visit may be performed on the day of the second bronchoscopy procedure. During the follow-up visit(s), the study coordinator will:

- Review the subject's compliance with study medication and assess alcohol use.
- Review the subject's alcohol intake and use of any other over-the-counter dietary or nutritional supplements.
- Review any adverse events or side effects from using study medications.
- Collect blood for alcohol level testing and biomarker testing (Follow-up Visit #1 only).
- Collect exhaled breath condensate using the procedure described above (Follow-up Visit #1 only).
- Compensate the subject for the visit with cash.

5.6 Second Bronchoscopy Procedure

- After at least two weeks of therapy with study medication (or placebo), the participants will undergo a repeat bronchoscopy procedure using the same method as described in section 5.3.1. Prior to the bronchoscopy, blood will be collected for serum zinc, blood alcohol, biomarker testing, and measurement of redox stress. Urine will be collected for ethyl glucuronide. Exhaled breath condensate will also be collected (described in section 5.4).

Subjects will again be compensated for undergoing the procedure, and the volunteer's driver will be offered a \$5 VA canteen voucher. No further clinical follow-up will be

performed after the second procedure, but the patient will receive a phone call within the next week to ensure no issues arise after completion of the study requirements.

6. Adverse Events and Serious Adverse Events

